### **4.9.3 Time to Response:**

Time to response (TTR) for the subset of patients who achieve a CR or PR will be summarized using descriptive statistics.

### **4.9.4 Progression-free Survival**

Progression-free survival is defined as the interval between the date of first dose and the date of disease progression (based on radiographic or clinical progression at EOT/EOS) or death, whichever occurs first. Patients who have the event after the start of subsequent anticancer therapy/procedure, or who are progression-free and alive at the time of clinical cutoff, or have unknown status, will be censored at the time of their last valid disease assessment on or before the start of subsequent anticancer therapy/procedure or clinical cut-off.

Patients with no post-baseline disease assessment will be censored on Day 1.

PFS will be estimated and displayed by dose levels for the efficacy analysis set using Kaplan-Meier methods (SAS® PROC LIFETEST). Patients who do not have a PFS event during or after the study will be censored. A Kaplan-Meier plot will be presented.

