5.1.5 End of Treatment Visit

The following procedures will be performed as soon as possible after decision to discontinue the study drug and prior to initiation of anticancer treatment:

- Serum or urine pregnancy test.
- Physical examination, including neurological examination and including whole body skin assessment. Whole body skin assessment does not have to be performed by a dermatologist; however, any unexplained lesion will be referred to a dermatologist for further evaluation and skin biopsy, if clinically warranted. The examination must include a determination if the patient has had any infection. At the discretion of the investigator, evaluation of any reported infection must be conducted to rule out infection with a microorganism that may be associated with autoimmune or neurological disease(s) as specified in the exclusion criteria.
- Vital sign measurements.
- ECOG performance status.
- Weight
- Disease assessments:
 - Patients who already have documented objective disease progression do not need to have assessments repeated.
 - Patients who do not already have documented objective disease progression will have assessments performed at the end of treatment visit if the most recent disease assessment was > 9 weeks prior to the end of treatment visit.
- Hematology.
- Coagulation panel.
- Biochemistry.
- Urinalysis.
- Additional renal function studies.
- 12-lead ECG.
- Sample collection for central laboratory assessment of PK, [REDACTED], ADA, and [REDACTED]
- Sample collection and shipment for PBMC subset analysis (only in Study Part 2).
- AE collection (collected until 84 days [12 weeks] after last dose of study drug).
- Concomitant medication use.

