8.4 Analysis Sets

Five analysis sets will be used in this study:

- The Safety analysis set consists of all patients who receive study drug
- The DLT-evaluable analysis set consists of all patients in Part 1 who receive study drug and excludes patients who discontinue from the study during the first 21-day cycle without experiencing a DLT.
- The Efficacy analysis set will consist of all patients with valid baseline data who receive at least 2 doses of study drug or who have documented progression of disease at any time after the first dose of study drug. Patients who do not have a post baseline assessment due to early clinical progression, toxicity, or death will also be included.
- The PK analysis set consists of all patients who receive study drug and have sufficient concentration data for PK analysis.

- The pharmacodynamic analysis set consists of all patients who receive study drug and have sufficient concentration data for pharmacodynamic analysis.

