8.6.1.4 Progression-Free Survival

Progression-free survival will be defined as the time from first dose of study drug until the first date of either disease progression or death due to any cause. The date of disease progression will be defined as the earliest date of radiological disease progression as assessed by the Investigator using the 2014 Lugano Classification for response for Hodgkin and Non-Hodgkin Lymphoma² ([Appendix 13.2](#)) or Global Response Score criteria for disease

progression for CTCL ([Appendix 13.3](#)). Patients with stable disease / without disease progression, or patients with death after an extended loss to follow-up, will be censored at the date of the last adequate disease assessment prior to the extended loss to follow-up. Further details on censoring rules will be outlined in the SAP.

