#### 4.1.3 Efficacy Analysis Set

The efficacy analysis set consists of patients who receive at least one dose of ADCT-301 with a valid baseline and at least one valid post-baseline disease assessment or patients who have documented progression of disease or death at any time after the first dose of study.

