### **4.9.5 Overall Survival**

Overall survival is defined as the interval between the date of first dose and the date of death from any cause. Patients who are known to be alive as of their last known status will be censored at their date of last contact. Patients who are lost to follow-up will be censored at the date the patient is last known to have been alive. The last confirmed alive date is the latest of the following: study visit date, telephone contact date, end of study last confirmed alive date, follow-up systemic (anticancer) therapy end date or start date (if ongoing or end date is missing), local or central radiologist scan date, or other date in the clinical database.

OS will be estimated and displayed by dose levels for the efficacy analysis set using Kaplan-Meier methods (SAS® PROC LIFETEST). A Kaplan-Meier plot will be presented.

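### The SAP's Day 1 censoring rule for PFS makes no exception for patients who progressed clinically or died without a post-baseline assessment

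*SAP*

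**What the plan says.** SAP 4.9.4 measures PFS from first dose to "the date of disease progression (based on radiographic or clinical progression at EOT/EOS) or death, whichever occurs first". Its main censoring sentence covers three situations: an event after subsequent anticancer treatment, a patient alive and progression-free at cut-off, and unknown status. All three are censored at the last valid disease assessment. A separate one-sentence paragraph follows: "Patients with no post-baseline disease assessment will be censored on Day 1". The next paragraph places the analysis in the efficacy set, by dose level, and adds: "Patients who do not have a PFS event during or after the study will be censored".

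SAP 4.1.3 defines that set as treated patients with a valid baseline and at least one valid post-baseline assessment, "or patients who have documented progression of disease or death at any time after the first dose of study".

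Protocol 8.6.1.4 defines PFS as "time from first dose of study drug until the first date of either disease progression or death due to any cause". It has no Day 1 rule and leaves further censoring detail to the SAP. SAP 3.3, which lists changes to the protocol's statistical section, mentions only the efficacy set.

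**The concern.** A patient who dies or progresses clinically before any post-baseline assessment meets both the event definition and the Day 1 rule. The SAP does not say which prevails. If the programmer follows the Day 1 sentence as written, the earliest failures become censorings at time zero. That is informative censoring, and it always pushes the curve upward.

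OS, analysed in the same set, is "the interval between the date of first dose and the date of death from any cause" and has no such rule, so the same deaths count there on their own dates. The reported PFS curve could then lie above the OS curve for the same patients, which cannot happen with correctly coded data. PFS is one of the named activity measures and is shown by dose level in small groups, where one or two patients move the curve visibly.

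**Working it through.** Neither document states a PFS estimate or an expected event count, so there is no planned figure to reproduce. The check is a reading of the text followed by Kaplan-Meier arithmetic.

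**Who the rule reaches.** Under SAP 4.1.3 a patient with no valid post-baseline assessment is in the efficacy set only because of documented progression or death. Radiographic progression is itself a post-baseline assessment, so the patients left are unassessed clinical progressions and unassessed deaths. SAP 4.9 takes clinical progression from the end-of-treatment/study disposition page, so it can be recorded with no assessment. The one patient in the set for whom Day 1 censoring is proper is an unassessed patient whose only event came after new anticancer treatment.

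**Whether such patients are expected.** Protocol 8.4 anticipates them: "Patients who do not have a post baseline assessment due to early clinical progression, toxicity, or death will also be included". The first scheduled assessment is at 6 weeks (Protocol 7.1). Without documented progression, an end-of-treatment assessment is required only "if the most recent disease assessment was > 9 weeks prior to the end of treatment visit". The screening assessment falls on Day -28 to -1. Nine weeks is 63 days, and there is no Day 0:
- from Day -28, 63 days later is Day 36;
- from Day -1, 63 days later is Day 63.

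So a patient who stops before about Day 36 to 63 with only a screening assessment need not have one at end of treatment.

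**Size, closed form.** Let a share q of a dose level have an unassessed early event, with no other early censoring. Once those events have passed, the correct estimate is S(t) = (1-q) × R(t), where R(t) is the curve of the remaining patients. With Day 1 censoring the affected patients never contribute to the risk set, so the reported curve is R(t) = S(t)/(1-q). The documents do not give q; the values below are assumptions.

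| q (assumed) | 1/(1-q) | true 50% reads as |
|---|---|---|
| 5% | 1.05 | 53% |
| 10% | 1.11 | 56% |
| 20% | 1.25 | 63% |
| 30% | 1.43 | 71% |

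In a Part 2 cohort of about 10 (Protocol 8.3), one such patient gives 10/9 = 1.11 and two give 10/8 = 1.25.

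**Worked example, n = 10.** Illustrative event days: 20 and 30 (unassessed deaths), then 42, 42, 84, 84, 147, 147, 210, 210. For OS, the other eight are assumed alive at Day 41.

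| Time | PFS, deaths counted | PFS, rule as written | OS |
|---|---|---|---|
| Day 41 | 8/10 = 80% | 8/8 = 100% | 80% |
| Day 42 | 6/10 = 60% | 6/8 = 75% | – |
| Day 84 | 4/10 = 40% | 4/8 = 50% | – |

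**Second example, n = 60** (all of Part 2, if treated at one dose level). Assume 12 unassessed events at week 3 and the other 48 events at exponential quantiles with a median of 12 weeks beyond week 6. Counting the early events gives 60 events, week-6 PFS 48/60 = 80%, week-12 PFS 34/60 = 56.7% and a median of 13.9 weeks. Under the literal rule there are 48 events, with 48/48 = 100%, 34/48 = 70.8% and 17.6 weeks.

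**The case against.** The strongest reply is that the sentence has been detached from its context. The preceding sentence says who is censored and sets the date as the last valid assessment. The Day 1 sentence can be read as supplying that date when no assessment exists. A death or clinical progression before new treatment fits none of the three censored situations and so stays an event. SAP 3.3 added death to the efficacy set definition, and SAP 4.9 and 4.9.4 bring clinical progression into the endpoints, so the sponsor evidently wants these events counted. On this reading the rule still has work to do, namely the event after new treatment.

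This is a plausible account of intent, but the SAP does not state it. The Day 1 sentence carries no condition and no link to the preceding one. Saying that patients without an event are censored does not say that patients with an event are not.

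Other points stand in part:
- Protocol 5.1.6 continues scans about every 12 weeks after discontinuation without objective progression. Some clinical progressors will therefore get a later assessment and escape the rule. Early deaths, and progressors who start new treatment unassessed, will not.
- A patient who left for toxicity alone, with no assessment, progression or death, is in the protocol's efficacy set but not the SAP's, so the affected group is narrower than the Protocol 8.4 wording.
- Protocol 8.6.1.4 itself censors deaths after extended loss to follow-up, and it dates progression radiologically. The conflict with the protocol therefore concerns deaths; the conflict over clinical progression is within the SAP.
- The size is hypothetical, because q and the event times are assumed.
- Derived PFS and OS data and all deaths are to be listed, so a misapplied rule could be traced.

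**Conclusion.** The concern holds. As written, SAP 4.9.4 gives two incompatible instructions for unassessed patients who progress clinically or die before new treatment, and the Day 1 instruction biases PFS upward. The factor is 1/(1-q) once the early events have passed, assuming no other early censoring: 1.05 to 1.43 for assumed q of 5% to 30%. What is certain is the missing exception; whether the bias occurs depends on how the sentence is programmed.

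The consequence is confined to a secondary, descriptive endpoint with no hypothesis testing. DLT, MTD and ORR results and error rates are untouched, as are dose levels with no such patients. It is still worth correcting before analysis, because the literal rule gives a wrong PFS curve and could place it above OS.

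**What to change.** Replace the Day 1 sentence in SAP 4.9.4 with wording to this effect: *A patient who has neither a post-baseline disease assessment nor a documented progression or death up to the earlier of new anticancer therapy/procedure and clinical cut-off is censored on Day 1. Where such a progression or death is documented, it is a PFS event on its own date, whether or not an assessment was made.*

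This keeps the legitimate use of the rule, for an unassessed patient whose only event followed new treatment. It is a change of one clause and needs no new data. If the rule was always meant as a fallback date, no result changes; otherwise PFS at the affected dose levels will look less favourable.

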### **4.9.5 Overall Survival**

Overall survival is defined as the interval between the date of first dose and the date of death from any cause. Patients who are known to be alive as of their last known status will be censored at their date of last contact. Patients who are lost to follow-up will be censored at the date the patient is last known to have been alive. The last confirmed alive date is the latest of the following: study visit date, telephone contact date, end of study last confirmed alive date, follow-up systemic (anticancer) therapy end date or start date (if ongoing or end date is missing), local or central radiologist scan date, or other date in the clinical database.

OS will be estimated and displayed by dose levels for the efficacy analysis set using Kaplan-Meier methods (SAS® PROC LIFETEST). A Kaplan-Meier plot will be presented.

## **5 Interim Analyses**

No formal interim analysis is planned.

## 6 Data handling conventions

### 6.1 General conventions

#### 6.1.1 Missing data

##### Handling of missing/partial dates

In general, imputation of missing dates will be made for AE onset date, AE resolution date, date of death, medication start/end dates, start and end dates of prior and subsequent therapies, and date of initial diagnosis for reporting. No imputation should be done at the data level.

- If dates are completely missing, no imputation will be made.
- For any partial date with missing year, no imputation will be made.
- For missing initial diagnosis date, if only day is missing, then the 1st of the month will be used; if only year is present, then Jan 1st will be used. If such imputed date for initial diagnosis is on or after date of first dose, then date of first dose - 1 will be used.
- If the imputed date is for an AE start date and is in the same year and month as but before the first dose date, then the first dose date will be used, or if the imputed AE start date is after the AE end date, then the AE end date will be used. If the imputed date is for an AE start date and is in the same year and month as but after the last dose date + 84 days, then the last dose date + 84 days will be used.
- If a medication date or time is missing or partially missing, so it cannot be determined whether it was taken prior or concomitantly, it will be considered as a prior and concomitant medication.
- If the imputed date is for a date of death and is before the last date that the patient is known to be alive, the latter date will be used.
- If the date part is missing for new anticancer therapy, the month and year will be used for comparison with disease assessment.

##### Handling of missing relationship to investigational product of TEAEs

If the assessment of the relationship to investigational product is missing, then the relationship to investigational product has to be assumed and the TEAE considered as such in the frequency tables of possibly related TEAEs, but no imputation should be done at the data level.

##### Handling of missing severity/grades of AEs

If the severity/grade is missing for one of the treatment emergent occurrences of an AE, the maximal severity of the remaining occurrences will be considered. If the severity is missing for all the occurrences a “missing” category will be added in summary table.

No other imputation of values for missing data will be performed.

### **6.1.2 Unscheduled visits**

Unscheduled visit measurements of laboratory data, vital signs, and ECG will be used for computation of baseline and worst values and/or grades. Re-windowing for unscheduled visits will not be performed

### **6.1.3 Duplicated visits**

Depending on the statistical analysis method, single values may be required for each analysis window. For example, change from baseline by visit usually requires a single value per visit. Unless otherwise noted throughout the rest of this document, when a single value is needed, the following rule(s) will be used:

- If more than 1 assessment occurs during the same nominal visit, select the record closest to the nominal day for that visit.
- If there are 2 assessments that are equidistant from the nominal day, the data of the assessment after the scheduled study day will be used.
- The last measurement will be used if multiple measurements are taken on the same day.

## Appendix 1 Glossary of Abbreviations

Glossary of Abbreviations:	
ADA	Anti-drug antibody
AE	Adverse event
AI	Accumulation index
AUC	Area under the concentration-time curve
CD	Cluster of differentiation
CI	Confidence interval
CL	Clearance
Cmax	Maximum concentration
CR	Complete response
CRM	Continual reassessment method
CRF	Case report form
CSR	Clinical study report
CTCAE	Common Terminology Criteria for Adverse Events
CTCL	Cutaneous T-cell lymphoma
DAR	Drug-to-antibody ratio
DESC	Dose Escalation Steering Committee
DLT	Dose-limiting toxicity
DOOR	Duration of response
ECG	Electrocardiogram
ECOG	Eastern Cooperative Oncology Group
EOS	End of study
EOT	End of treatment
HL	Hodgkin lymphoma
IP	Investigational product
MedDRA	Medical Dictionary for Regulatory Activities
mSWAT	modified Severity-Weighted Assessment Tool
MTD	Maximum tolerated dose
NE	Not evaluable
NHL	Non-Hodgkin lymphoma

ORR	Overall response rate
OS	Overall survival
PBD	Pyrrolobenzodiazepine
PD	Pharmacodynamics, progressive disease
PFS	Progression-free survival
PK	Pharmacokinetic
PR	Partial response
PT	Preferred term
QTc	Corrected QT interval (ms)
SAE	Serious adverse event
SAP	Statistical analysis plan
SD	Stable disease
SMQ	Standardised MedDRA Query
SOC	System organ class
SPD	Sum of product of diameters
std	Standard deviation
TEAE	Treatment-emergent adverse event
TFLs	Tables, figures, and listings
TTR	Time to response
<math>\lambda_z</math>	Terminal elimination phase rate constant
Tmax	Time to maximum concentration
t1/2	Terminal half-life
Vss	Volume of distribution at steady-state
Vz	Volume of distribution
WBC	White blood cells
WHO-DD	World Health Organization-Drug Dictionary
